There will be a total of 24 subjects (power calculation was established at 10 patients per group, however, after considering the expected 20% dropout rate, 12 patients will be included in each group with at least one implant presenting peri-implantitis that meets the inclusion criteria. Twelve patients will be randomly allocated for each group. The control group will be treated with flap surgery, including implantoplasty of the implant surface above the interproximal bone level, debridement of osseous defect, and the implant surface with periodontal cures; followed by human allograft placed in the defect and protected by collagen membrane. This procedure is the current standard of care. The test group will be treated the same as the control group with the aid of the laser application (Er:YAG), which is also routinely used in such treatment for clinicians who have access to dental lasers.

B. Study settings

This investigation will be conducted in the Department of Periodontics and Oral Medicine at the U-M School of Dentistry, Ann Arbor, Michigan, USA.

C. Eligibility

1. Pre-Screening Examination

In order to identify potentially eligible subjects, the electronic database will be screened for the procedure code D6010, which corresponds to surgical placement of endosseous dental implants. All electronic records initially retrieved with the automated query, will be manually reviewed by study team members for inclusion and exclusion criteria in order to confirm eligibility of each subject. If they qualify, the subjects will receive an invitation letter requesting that they contact the study coordinator by telephone for information regarding participation in the study. In addition, the study coordinator will conduct a follow-up telephone call approximately two weeks later to the subjects receiving the invitation letter to inquire their potential interest to participate in the study. The study coordinator will perform a brief telephone interview to determine whether or not the patient will qualify based on age and basic inclusion and exclusion criteria. Subjects indicating they may qualify would be scheduled for a screening examination appointment. In addition, a flyer will be posted in all of the clinics at the University of Michigan School of Dentistry.

2. Screening Examination V0

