PICF samples will be obtained at Pre-surgical Preparation (V1), 2 week (V3), 4 week (V4), 12 week (V5) and re-evaluation-24 week (V6). These samples will be used for bacterial DNA and biomarker analysis. Samples will be collected with sterile paper point and strips. The sites sampled will be isolated with cotton rolls to keep the area dry and free of salivary contamination. A gentle air blow will be applied perpendicularly before sampling. For biomarker analysis, a perio strip will be inserted into the crevice until mild resistance is felt and left for 30 seconds. For microbial profile, a paper point will be inserted for 10 seconds. Two sampling per assays will be collected with 90-second intervals. The paper point and paper strip will be carefully removed to avoid contamination from contact with other tissues and to avoid trauma to the site. The samples will then be transferred to sterile micro centrifuge tubes containing protease inhibitors and stored at – 80 °C until further processing of the biomarkers analysis. All

the sampling procedures are established and published by our group (Kinney et al. 2014; Wang et al. 2016).

Examiners calibration

Calibration of the examiner will be performed through a training exercise with a calibrated examiner prior to the beginning of the study. The calibrated examiner will observe and confirm the accuracy of the clinical measurements of PI, GI, and PD of the study examiner (>0.8 agreement between examiners will be considered calibrated).

IV. Statistical Analysis: Sample Size

This study will have a sample size of 24 subjects, 12 in each of the groups.

The study power was calculated using the software nQuery Advisor v7.0 (Statistical Solutions, Saugus MA, USA). A difference of 2.0mm between groups was considered as clinically significant. The power value was evaluated for probing depths at 6 months after the surgery. A “p” value of less than 0.05 will be considered statistically significant.

Data Analysis

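### Twelve per group allows for 16.7% dropout, not the stated 20%; protecting 10 completers would take 13, and the effect on power is small

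*Combined protocol and SAP*

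**What the plan says.** All references are to the combined protocol and SAP.

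- **Section III.A (Trial design)** gives the size before dropout: "power calculation was established at 10 patients per group". It then gives the enrolled size: "after considering the expected 20% dropout rate, 12 patients will be included in each group".
- **Section IV (Statistical Analysis: Sample Size)** repeats the enrolled size: "This study will have a sample size of 24 subjects, 12 in each of the groups". It names the effect, "A difference of 2.0mm between groups was considered as clinically significant", and the endpoint, "The power value was evaluated for probing depths at 6 months after the surgery". The only error rate given is a p "value of less than 0.05 will be considered statistically significant".
- Section IV names the software but gives no SD, target power or sidedness.
- **Section V, under discontinuation and replacement of subjects**, rules out replacing those who stop for adverse events. It does not address replacement for other reasons. It also asks that participants who are withdrawn have the end-of-study evaluations.

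**The concern.** The plan ties three numbers together: 10 needed, 20% expected to be lost, 12 enrolled. Read together, they say that 12 per group will still leave the powered 10 after the expected losses. They do not fit. Twenty percent has been added to the 10, whereas the loss is taken from the number enrolled.

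At stake is whether the dropout statement is true, and whether a reader who takes the trial to be powered at 10 per group under the plan's own dropout assumption is being told something slightly too favourable.

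**Working it through.** **Inputs from the documents.** 10 per group for power, 20% dropout and 12 per group enrolled (section III.A); 2.0 mm difference in probing depth at 6 months and a 0.05 significance level (section IV).

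**Assumed, because not stated.** Target power of 80% or 90%; a two-sided two-sample t-test; for the retention figures, each patient lost independently with probability 0.20.

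**1. The plan's own figure.** 10 × (1 + 0.20) = 12. This reproduces the stated 12 exactly.

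**2. The inflation that protects 10.** n / (1 − d) = 10 / 0.80 = 12.5, rounded up to 13 per group (26 in total).

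**3. What each size leaves.**
- 12 × 0.80 = 9.6 expected completers per group, 0.4 short of 10.
- 13 × 0.80 = 10.4.
- Largest loss that 12 can take and still keep 10: 2 / 12 = 16.7%.

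**4. Chance of keeping at least 10.**
- With 12 enrolled, P(X ≥ 10) for X ~ Binomial(12, 0.8) is 0.2835 + 0.2062 + 0.0687 = 0.558. For both groups it is 0.558² = 0.312.
- With 13 enrolled it is 0.747, and 0.747² = 0.558 for both.

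| Enrolled per group | One group keeps ≥ 10 | Both keep ≥ 10 |
|---|---|---|
| 12 | 56% | 31% |
| 13 | 75% | 56% |

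**5. Effect on power.** Solve for the SD at which 10 per group has the assumed power for 2.0 mm, then hold it fixed and change n. Power comes from the noncentral t distribution with noncentrality 2.0 / (SD × √(2/n)) and 2n − 2 degrees of freedom.
- For 80% at n = 10, the SD is 1.51 mm (noncentrality 2.96, critical t 2.10 on 18 df). At n = 9.6 the noncentrality is 2.90, and at n = 9 it is 2.81.
- For 90% at n = 10, the SD is 1.30 mm (noncentrality 3.43). At n = 9.6 it is 3.36, and at n = 9 it is 3.25.

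The averaged rows weight the power at each pair of completer numbers by its binomial probability.

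| Patients per group | If sized for 80% (SD 1.51 mm) | If sized for 90% (SD 1.30 mm) |
|---|---|---|
| 10 completers | 80% | 90% |
| 9.6 completers (expected from 12) | 78.2% | 88.6% |
| 9 completers | 75.1% | 86.3% |
| 12 enrolled, averaged over random 20% loss | 77.3% | 87.7% |
| 13 enrolled, averaged over random 20% loss | 80.9% | 90.4% |

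**The case against.** The strongest reply is that this is a rounding-scale matter. Patients come in whole numbers, and two losses from 12 leave exactly 10. Under the binomial model used above, 10 is both the most likely and the median number of completers. The corrected enrolment is one more patient per group. Withdrawn participants are meant to have end-of-study evaluations, and only adverse-event discontinuations are barred from replacement, so a withdrawal need not mean a lost measurement. All of this bears on size and it stands, with one limit: an evaluation done early is not the 6-month probing depth that was powered, and patients lost to follow-up supply none.

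The retention percentages also need their comparator. A 56% chance of keeping 10 in a group sounds alarming, but the correct formula gives only 75%. Much of the risk is chance variation in small groups that 13 per group would also carry.

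Two stronger readings are tempting, and the documents support neither.
- A reader might infer that the powered size will not be reached, or that the trial is materially underpowered. The expected shortfall is 0.4 of a patient per group, and 10 per group are kept whenever no group loses more than two.
- A reader might infer that the allocation rule in section III.D adds to the shortfall by leaving an 11/13 split. Sections III.A, III.D and IV all fix 12 per group, so that split arises only if the target is ignored. Even then, 20% loss leaves 8.8 and 10.4, with power of 77.9% against 78.2% at 9.6 each under the 80% assumption, a difference of 0.3 points.

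None of this makes the dropout statement true.

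**Conclusion.** Wrong as written, minor. The figure of 12 comes from multiplying by 1.2 where dividing by 0.8 was needed. That conclusion rests on the plan's own numbers alone. Twelve per group covers 16.7% loss, not 20%.

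The cost in power at the expected 9.6 completers is 80 − 78.2 = 1.8 points or 90 − 88.6 = 1.4 points. Averaged over random dropout it is 80 − 77.3 = 2.7 or 90 − 87.7 = 2.3 points. If each group falls to 9, it is 4.9 or 3.7 points.

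These power figures depend on the assumed targets, the two-sided t-test and the SDs solved from them. They measure the effect of the slip relative to whatever was planned. They do not show what the trial's power actually is, because the 10 itself cannot be reproduced without the SD and target power.

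**What to change.** Keep 24 patients and change the text in two places.

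1. In section III.A, replace the dropout statement with: *12 per group allows for 2 losses per group (16.7%); at 20% loss about 9 to 10 per group remain.*
2. In section IV, state the SD, target power and sidedness that produced 10 per group, and quote the power at 9 to 10 per group.

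No patients, visits or procedures are added. The price is that the stated dropout allowance and the quoted power become slightly less favourable. Enrolling 13 per group (26 in total) would make the 20% statement correct on expectation, but a gain of about 3 to 4 points in averaged power (77.3% to 80.9%, or 87.7% to 90.4%) is not needed to put the text right.

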Subjects will be randomized into one of the two groups. Twelve subjects will be allocated to the test group and another 12 subjects to the control group. The subject will not know which group he or she belongs as blinded allocation. Randomization will be determined by the last digit of the chart number (odd number goes to Group A and even number goes to Group B) but if one group has two subjects more than the other group, the next subject will automatically be enrolled in the lesser number group to ensure timely even distribution. The assignment of control or experimental group to Group A or B will be written by the primary surgeon (Principle Investigator) in a concealed envelop before recruiting patients. This ensure the clinical examiner be blinded throughout the study. This randomization will prevent any operator bias.

E. Pre-surgical Preparation V1

Prior to the surgical visit, the subject will be asked if they are still willing to participate in the study and their medical history will be reviewed. Clinical measurements of PD, BOP, CAL, PI and GI will be recorded and peri-implant bacterial and crevicular fluid samples will be collected. A prophylaxis or a periodontal maintenance will be completed based on the subject's prior diagnosis. In addition, a set of intraoral photographs will be taken, one standardized peri-apical radiograph, and maxillary and mandibular impressions will be taken. Articulating paper will be used to check the occlusal contact of the implant crown, if there is obvious heavy contact or lateral interference, occlusal adjustment will be made.

F. Surgical procedure V2

The subject will be asked if they are still willing to participate in the study and their medical history will be reviewed. The subject's vitals of blood pressure and heart rate will be taken. During this visit, intraoral photos will be taken and all surgeries will be performed under local anesthesia using one or more of the following medications:

- Lidocaine with epinephrine, (Xylocaine 2%®-Epinephrine 1:100,000 and 1:50,000, Dentsply Pharmaceutical, York, PA, USA).
- Articaine (Septanest 4%®-Epinephrine 1:100,000, Dentsply Pharmaceutical, York, PA, USA).
- Mepivacaine (Polocaine 2%®-Levonordefrin 1:20,000, Dentsply Pharmaceutical, York, PA, USA).

After local anesthesia, the width of the keratinized tissue around the implant will be measured by periodontal probe and the thickness of the peri-implant mucosa will be measured with endo file and stopper.

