CRFs will be signed and dated by the investigator or a designated representative and filled out in black ink. If an entry on a CRF requires change, the correction will be made as follows:

- a. A single line will be drawn through the incorrect entry.
- b. The date will be entered and the change initialed. White-out or erasure on CRFs will not be permitted under any circumstance.

All fields and blanks must be completed. The following abbreviations will be used when values or answers cannot be provided: NA=not applicable; ND=not done, UNK=not known

Completed original CRFs will be collected by the Principal Investigator. CRF must be submitted for each subject.

Data entry will proceed directly from the case report form. The data, as well as group/subject identification, will be made available to the investigator at the conclusion of the study.

4. Study monitoring

The investigator will periodically audit all CRFs and corresponding portions of U-M School of Dentistry records of each study participant and has a monitoring plan with the U-M Institutional Review Board. The monitoring will provide the Principal Investigator the opportunity to evaluate the progress of the study and to verify the accuracy and completeness of the CRFs; assure that all protocol requirements, applicable FDA regulations and investigator's obligations are being fulfilled, and to resolve any inconsistencies in the study records. The Principal Investigator may stop the study if it is observed that the protocol or sound clinical practices are not being followed. The Principal Investigator may exclude subjects from the study if review of their records indicates violations of the protocol or if there are other reasons to believe that their inclusion would jeopardize the validity of the study.

B. Regulatory Considerations

1. Institutional Review Board (IRB)

The protocol and informed consent for this study must be reviewed and approved by an appropriate IRB before enrollment of participants into the study.

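### Allocation by chart-number parity with a forced catch-up step is quasi-random and not concealed at enrolment: staff can foresee the group letter, and the principal investigator can foresee the arm

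*Combined protocol and SAP*

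**What the plan says.** The General Investigation Plan calls the study a double-blinded randomised controlled trial, and section III.D plans 12 patients per group. The same section gives the allocation method: "Randomization will be determined by the last digit of the chart number", odd to A and even to B. It then adds an override: "if one group has two subjects more than the other group, the next subject will automatically be enrolled in the lesser number group".

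Which letter is the laser arm is fixed once for the whole trial. That code "will be written by the primary surgeon (Principle Investigator) in a concealed envelop before recruiting patients". The stated purpose is examiner masking: "This ensure the clinical examiner be blinded throughout the study". The section ends by asserting that the scheme rules out bias on the operator's part.

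Two other places matter. Under Pre-Screening Examination (III.C.1), the retrieved electronic records "will be manually reviewed by study team members for inclusion and exclusion criteria", and this happens before the invitation letter goes out. Under Study monitoring (section V), the principal investigator may exclude subjects after reviewing their records, either for protocol violations or because keeping them is thought to threaten the study's validity.

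No section describes a random sequence, an independent allocator or concealment patient by patient.

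**The concern.** Randomisation protects a comparison only if nobody who influences entry or retention can tell what the next assignment will be. Here the assignment is a fixed function of two visible things, the chart number and the current group counts.

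Several entry and retention decisions leave room for judgement. The exclusion criteria include obvious malpositioning of the implant and any medical condition that might influence the outcome. The premature exclusion criteria let the researcher remove a subject on best-interest grounds, and the Study monitoring text adds the principal investigator's power to exclude. If such a decision is made with the arm in view, defect severity or prognosis can differ between arms before treatment starts.

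The Data Analysis section specifies no adjustment for baseline severity, and adjustment could not repair selection on unmeasured features. Every between-group comparison in the trial rests on this step.

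**Working it through.** The plan gives no figure for predictability. Its only number here is the intended 12 and 12.

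**Inputs.** From III.D: 24 patients, the parity rule, the forced assignment at a difference of two, and one A/B code written by the principal investigator. Assumption: odd and even last digits are equally likely. A 60:40 mix is used as a sensitivity check.

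**Step 1: is any step random?** With a difference of 0 or 1, the letter equals the parity of the digit. With a difference of 2, the letter is that of the smaller group. Both are deterministic given chart number and counts, so the next letter is fixed for 24 of 24 patients at the moment each one is considered.

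**Step 2: how often do the counts alone decide?** Let D be the absolute difference between groups.
- After any odd number of patients, D = 1.
- From D = 1, the next patient takes D to 0 or to 2, each with probability 0.5. So after any even number of patients (2, 4, …, 22), P(D = 2) = 0.5.
- A forced assignment can therefore fall on patients 3, 5, …, 23, which is 11 occasions.
- Expected forced assignments = 11 × 0.5 = 5.5, or 5.5/24 = 23%.
- The digit settles the remaining 24 − 5.5 = 18.5.
- With a 60:40 mix of digits, exact enumeration gives 5.9 forced assignments.

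Someone who knows the counts but not the chart number would guess 5.5 + 18.5 × 0.5 = 14.75 of 24 letters correctly (61%).

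**Step 3: what does the digit alone give?** When the catch-up rule applies, the digit points to the wrong group half the time: 5.5 × 0.5 = 2.75 patients. Parity without the counts therefore gives 24 − 2.75 = 21.25 of 24 letters on average.

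**Step 4: who can foresee what?**

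| Person | Has | Can foresee before enrolment |
|---|---|---|
| Staff reviewing records, without the code | Chart number; counts if kept informed | Group letter |
| Principal investigator / primary surgeon | The code; letter from chart number and counts | Arm |
| Anyone who learns the code | The code | Arm of each patient whose letter they know |

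**Step 5: what does the envelope conceal?** It holds one letter-to-arm code, not one assignment per patient. It hides the arm from people who have not seen it, which is an aid to masking. It hides nothing from its author, and it does not hide the letter from anyone.

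**The case against.** The best defence is that the envelope separates letter from arm. III.C.1 gives record review to study team members and invitation and telephone screening to the coordinator, and nothing says that they know the code. On that reading, those who recruit foresee only A or B. This stands, and it narrows the point: foreknowledge of the arm is shown only for the principal investigator, and the best-documented route is that person's power to exclude. A part in recruitment is not stated. The sham laser set-up in the surgical section also supports patient masking, which this defect leaves intact.

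Several stronger readings are tempting but not supported:

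- *That the principal investigator knows every arm from the outset.* The catch-up rule depends on enrolment order and overrides parity for about 2.75 of 24 patients. The arm is foreseeable only as each patient comes up.
- *That one unmasked patient unmasks all 24.* This needs every letter to be known. The digit alone gives about 21.25, and the documents do not say whether the examiner sees chart numbers or what identifier the case report forms carry.
- *That section V contradicts III.D.* Under Data reporting and case report forms: "The data, as well as group/subject identification, will be made available to the investigator at the conclusion of the study". This conflicts with III.D only if that investigator is the principal investigator. The text uses both terms, so it needs clarifying.
- *That the rule fails to deliver 12 and 12.* With no cap, the final split is 12:12 with probability 0.5 and 13:11 or 11:13 with probability 0.25 each. If the stated 12 per group is a cap, the count after 23 patients is 12:11 and the last patient always completes 12:12. A 13:11 split would matter little in any case.
- *That moving two or three patients is enough to create or erase an effect.* The plan gives no SD. Assume 1.6 mm, the value implied by 2.0 mm, 10 per group and an assumed 80% power at two-sided 0.05. With 12 per arm, significance then needs about 2.07 × 1.6 × √(2/12) ≈ 1.35 mm. Exchanging three patients per arm whose outcomes differ by 2 mm shifts the contrast by 3 × 2 × 2/12 = 1.0 mm; a 3 mm difference shifts it by 1.5 mm. The answer depends wholly on assumed values.

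**Conclusion.** The concern holds in this form. The allocation is quasi-random: the next letter is foreseeable for all 24 patients to anyone with the chart number and the running counts, and the arm is foreseeable to the principal investigator, who wrote the code. About 5.5 assignments (23%) follow from the counts alone if odd and even digits are equally likely. The deterministic nature of the rule does not depend on that assumption.

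The envelope may serve examiner masking but gives no concealment at enrolment. Because a single code covers the trial, a leak would reveal the arm of any patient whose letter is known. The randomised label and the assurance about operator bias are therefore unsupported as written.

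A reader might infer that selection will take place or that the result will be biased. The documents do not show this. They show only that nothing prevents it. The point should be fixed before allocation begins, because no later analysis can restore what the allocation step fails to provide.

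**What to change.** Amend III.D as follows:

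- Replace the parity and catch-up rules with a computer-generated permuted-block list, 12 per arm, with varying and undisclosed block sizes. It should be made by a person independent of recruitment, surgery and examination. The documents name no statistician, so the amendment should say who this is.
- Put each assignment in a sequentially numbered, sealed, opaque envelope. Open it at V2, only after eligibility is confirmed and the V1 measurements are locked.
- Delete the single A/B envelope.
- Use study IDs instead of chart numbers on examination forms.
- Delete the sentence on operator bias. Describe any patients already allocated under the present rule as quasi-randomised.
- In section V, state who receives group identification at the end of the study.

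The cost is a protocol amendment, 24 envelopes and a small amount of an independent person's time. It needs no extra patients or visits.

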1) Test and Control group procedures

Open flap debridement and regenerative approach will be the treatment of choice for both groups. Intrasulcular incisions will be performed with a 15-C scalpel around the

implant to expose the contaminated surface. All the suprabony implant surface will be debrided with implantoplasty procedure as a standard of care and the specific treatment and outcome will be focused on the infrabony component of the defect. The experimental group will have the same treatment as the control group, but the laser will be used as a tool to aid in tissue debridement. In control group, the laser will also be set up for a fake application.

(A) Control group:

After the reflection of the flap, removal of the granulation tissue and mechanical debridement of infrabony defect and the implant surface with mechanical scalers will be performed.

(B) Test group:

The same protocol for the control group will be completed with the addition of the Er:YAG laser application to assist in mechanical debridement of the osseous defect and detoxify the implant surface.

The granulation tissue within the peri-implant defect will be collected during the surgical debridement will be stored for Immunoscore analysis:

Next-gen RNA sequencing will be performed on the peri-implant granulation tissue. This additional protocol serves two important scientific goals. First, we have built a novel machine learning tool, characterization of immune cell subsets using RNA-Seq data (Ci-Seq). We will utilize Ci-Seq to comprehensively annotate the immune landscape of the granulation tissue. Specifically, we will resolve the percentages of different immune cell subsets and determine the weighted impact of each immune subset on the overall regenerative potential. Second, we will perform Gene Set Enrichment Analysis (GSEA) and differential genes expression profiling to identify key pathways that modulate patients' response to regenerative treatment.

2) Bone Graft and Membrane Placement (Both groups)

After detoxification of the implant surface, mineralized bone allograft will be applied to both groups to fill the peri-implant defects. After the graft material is properly placed, an

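### Equal mechanical debridement in the two arms is declared but neither protected nor measured, and randomization cannot prevent operator bias at this step

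*Combined protocol and SAP*

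**What the plan says.** On equality of the arms, Section III.A (Trial design) states "The test group will be treated the same as the control group with the aid of the laser application (Er:YAG". Section III.F, item 1 (Test and Control group procedures) repeats it: "The experimental group will have the same treatment as the control group".

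On what the laser does, the same item says "the laser will be used as a tool to aid in tissue debridement", and its test-group paragraph says "The same protocol for the control group will be completed with the addition of the Er:YAG laser application to assist in mechanical debridement". The Significance paragraph in Section II expects debridement to be easier with the laser.

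On the mechanical component, Section III.A names the work as "debridement of osseous defect, and the implant surface with periodontal cures", while the control-group paragraph of Section III.F says "mechanical debridement of infrabony defect and the implant surface with mechanical scalers will be performed".

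On blinding, the control arm has a sham: "In control group, the laser will also be set up for a fake application". Section III.D (Randomization) describes the subject and the clinical examiner as blinded. It also has the primary surgeon write, before recruitment, which of Groups A and B is experimental. Group membership follows the last digit of the chart number, with a rule that sends the next subject to the smaller group once the groups differ by two. The section ends: "This randomization will prevent any operator bias".

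**The concern.** Specific Aim 1 asks what the laser contributes compared with conventional mechanical debridement. That comparison is clean only if the mechanical work is the same in both arms, or if any difference is a defined part of the test treatment. Here the work is done by an operator who can know the arm beforehand, with no stated endpoint and no record of how much was done.

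Randomization balances the patients who enter the arms. It does not govern what an operator who knows the arm does afterwards, so this problem would remain under a perfect allocation scheme. A difference in probing depth or bone fill in either direction, or a null result, could partly reflect unequal debridement effort. With nothing recorded, no analysis could detect or describe it.

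**Working it through.** **Passages side by side**

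1. *Sequence.* The test-group sentence can be read as the full control procedure followed by the laser, or as the laser working during debridement. The phrase calling the laser a tool for tissue debridement favours the second reading; the word for addition favours the first. Nothing settles it. Two surgeons could follow the text and deliver different test treatments.
2. *Endpoint and record.* Neither arm has a completion criterion, a debridement time, or a laser or sham duration. Table I lists no such item for the surgery visit. The case report forms are not among the documents, but nothing in the protocol asks them to capture it.
3. *Who knows the arm.* The primary surgeon writes the A/B code. That code, the chart number and the running group counts give the arm. Whoever operates learns it at the latest when applying the live or sham laser.
4. *Who is blinded.* Subject and clinical examiner. No blinding of the operator is described.
5. *Instrument.* The two names differ between Sections III.A and III.F. Both describe the procedure that the arms share, so this creates no between-arm difference; it needs only a wording correction.
6. *Tissue for Aim 4.* Granulation tissue is collected during debridement, and Aim 4 asks whether the laser affects the immunoscore. Whether sampling comes before or after laser exposure is not stated.

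**Scale, as an illustration only**

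The plan has no figure for debridement. From Sections III.A and IV: 10 per group before dropout, a 2.0 mm difference in probing depth at 6 months, and a significance level of 0.05 (two-sided assumed). The enrolled number follows as 10 × 1.20 = 12. The SD and target power are not stated, so the 10 cannot be reproduced. Solving backwards with a t-test, 10 per group implies an SD of about 1.51 mm for 80% power or 1.30 mm for 90%. I take 1.5 mm as an assumption and 1.3 to 1.8 mm as a range.

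Noncentrality = shift / (SD × √(2/n)). With n = 10 and SD 1.5 the denominator is 1.5 × √0.2 = 0.671; df = 18 and the critical value is 2.101.

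*Less effective debridement in the test arm, true laser effect 2.0 mm:*

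| Assumed loss | Net effect | Noncentrality | Power, SD 1.5 | Power, SD 1.3 to 1.8 |
|---|---|---|---|---|
| 0 | 2.0 mm | 2.98 | 80.5% | 90% to 65% |
| 0.25 mm | 1.75 mm | 2.61 | 69% | 81% to 54% |
| 0.5 mm | 1.5 mm | 2.24 | 56% | 69% to 42% |
| 1.0 mm | 1.0 mm | 1.49 | 29% | 37% to 22% |

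*More effective debridement in the test arm, no laser effect (nominal chance of a significant result for the laser 2.5%):*

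| Assumed shift | Noncentrality | Chance, SD 1.5 | Chance, SD 1.3 to 1.8 |
|---|---|---|---|
| 0.25 mm | 0.37 | 5.4% | 6.0% to 4.8% |
| 0.5 mm | 0.75 | 10.5% | 12.6% to 8.5% |
| 1.0 mm | 1.49 | 29% | 37% to 22% |

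Every shift here is assumed. The tables show what a given imbalance would do, not that one will occur.

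**The case against.** The strongest reply is that the protocol says twice that the test arm receives the control treatment, so a reader who concludes that debridement will be unequal, or that the laser replaces part of the hand instrumentation, goes beyond the text. That is correct. Substitution is one reading of the words for assisting and aiding; it is nowhere stated. That the surgeon decides when debridement is finished is also an inference, from the missing criterion, and it assumes that the surgeon who wrote the code operates.

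Second, the objective in Section II is laser-assisted debridement and decontamination as a package. If the laser eases or displaces some hand work, that may be part of the treatment under test. This stands, but then the protocol should say so. It also does not cover effort in the control arm, which remains undefined.

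Third, the most natural behaviours are to debride longer when no laser will follow, or more briefly when it will. If more debridement helps, both work against the laser, and a positive result would be conservative. That is fair, and it makes the power table the more relevant one for those behaviours. The documents do not fix the direction, however: an operator who expects the laser to work could be more thorough in the test arm.

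Fourth, it would be wrong to infer that the sham leaves only the patient blinded. The examiner is separately described as blinded, so the gap is performance by the operator, not measurement.

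**Conclusion.** The concern holds in a limited form. Equality of mechanical debridement is declared, but it is not defined, masked from the operator or recorded. The claim that randomization prevents operator bias is unsupported for the operative step. The documents do not show that the arms will differ, and they give no debridement times or effects from which a difference could be sized.

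The exposure covers all 24 operations. The conclusion rests on the operator knowing the arm before debridement ends, which the surgeon-written code and the chart-number rule make possible, and on the absence of any endpoint or record in the protocol text. This should be corrected, because the remedy is cheap and the problem cannot be repaired at analysis. It does not by itself invalidate the comparison.

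**What to change.** 1. **Reconcile the wording.** Make Sections III.A and III.F agree on whether the laser follows or accompanies mechanical debridement, and on the instrument named. The choice is the sponsor's. It should be consistent with when tissue is sampled for Aim 4.
2. **Mask the operator for as long as the sequence allows.** Have an existing team member other than the surgeon hold concealed per-subject assignments, replacing the single A/B code and the chart-digit rule. Open each one in surgery only when the reconciled sequence reaches the live or sham laser step. The present balancing rule should not be carried over, because an operator who knows past arms could predict the next one whenever the groups differ by two.
3. **Measure it.** Record debridement minutes, laser or sham minutes and declared completion on the case report form in both arms, and report them by arm.
4. **Correct the claim.** Delete the operator-bias sentence in Section III.D, or limit it to what the design supports.

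Cost: the allocation procedure must be rewritten and a few form fields added. The laser is already set up in both arms, so no equipment is needed. If the sponsor chooses laser after debridement, the estimate applies to that sequence, and tissue removed before the laser cannot show a laser effect for Aim 4. If the sponsor chooses concurrent use, the work done after the assignment is opened is unmasked, and the recorded minutes are the only check on it.
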